6.1.1. Encorafenib 75 mg hard capsule

Encorafenib will be prepared in oral hard capsules.

Code and name: W0090-Encorafenib for Europe, LGX818-Encorafenib for US and Japan.

Encorafenib may also be known as ONO-7702 in Japan.

Pharmaceutical presentation: hard capsule of 75 mg

Composition:

- Hard capsule
 - **Active ingredient:** Encorafenib
 - **List of Excipients:** copovidone, Poloxamer 188, cellulose microcrystalline, succinic acid, crospovidone, silica colloidal anhydrous, magnesium stearate of vegetable origin.
- Capsule shell (gelatin, titanium dioxide (E171), iron oxide red (E172), iron oxide yellow (E172), iron oxide black (E172), ink capsule shell (Pharmaceutical Glaze, iron oxide black (E172), Propylene glycol).

6.1.2. Binimetinib 15 mg film-coated tablet

Binimetinib will be prepared in film-coated tablets for oral use.

Code and name: W0074 - Binimetinib for Europe, MEK162 - Binimetinib for US and Japan.

Binimetinib may also be known as ONO-7703 in Japan.

Pharmaceutical presentation: film-coated tablet of 15 mg

Composition:

- Film-coated tablet

- **Active ingredient:** Binimetinib
- **List of excipients:** lactose monohydrate, microcrystalline cellulose, croscarmellose sodium, magnesium stearate, colloidal silicon dioxide/silica colloidal anhydrous, OPADRY® yellow 85F92213 (polyvinyl alcohol – part hydrolyzed, macrogol / PEG 3350, titanium dioxide, talc, iron oxide yellow E172, iron oxide black E172)

6.1.3. Cetuximab solution for infusion

Cetuximab is available under different formulations:

- 1 formulation for Europe and Japan
- 1 formulation for US
- **Europe and Japan formulation: ERBITUX® 5 mg/mL solution for infusion**

Cetuximab solution for infusion will be supplied in labelled packages : single-use vial of 500 mg cetuximab (5 mg/mL solution) – vial of 100 mL

Cetuximab is a colorless solution administered intravenously.

Cetuximab is a chimeric monoclonal IgG1 antibody produced in a mammalian cell line (Sp2/0) by recombinant DNA technology.

Composition:

- **Active ingredient:** Cetuximab 5 mg/mL
- **List of excipients:** Sodium chloride, Glycine, Polysorbate 80, Citric acid monohydrate, Sodium hydroxide, Water for injection.

Cetuximab does not contain any antimicrobial preservative or bacteriostatic agents. From a microbiological point of view, the product should be used immediately after opening. If not used immediately, in-use storage times and conditions prior to use are the responsibility of the user and would normally not be longer than 24 hours at 2 to 8°C, unless opening has taken place in controlled and validated aseptic conditions.

- **US formulation**

Erbix®(cetuximab) in the US is commercially available and is supplied at a concentration of 2 mg/mL as a 100 mg/50 mL, single-use vial or as a 200 mg/100 mL, single-use vial as a sterile injectable liquid containing no preservatives.

Composition:

Cetuximab is formulated in a solution with no preservatives, which contains:

- **Active ingredient:** Cetuximab 2 mg/mL
- **List of excipients:** sodium chloride, sodium phosphate dibasic heptahydrate, sodium phosphate monobasic monohydrate, and Water for Injection

6.2. PACKAGING AND LABELLING

In Europe, the treatment units will be packed and labelled by the Investigational Medicinal Product Management Service of IRPF according to the European Directive, local requirements and local languages.

In US, the treatment units will be packed and labelled within US by the sponsor designee and comply with the legal requirements of the US.

In Japan, the treatment units will be packed and labelled by sponsor designee and comply with the legal requirements of Japan.

6.2.1. Packaging**6.2.1.1. Encorafenib 75 mg capsule**

- **Europe formulation**

- Primary packaging

- 70 hard capsules will be packaged in a bottle 175 cc (HDPE, white, opaque, square) closed with a cap (38 mm, polypropylene (PP), white, child-resistant design, cap with induction seal liner) and containing a 2 grams silica gel desiccant.

- Secondary packaging (only for Europe)

- The bottle will be packaged in a sealed box.

- **US and Japan formulation**

- Primary packaging

- 70 hard capsules will be packaged in a bottle 175 cc (HDPE, white, opaque, square) closed with a cap (38 mm, PP, white, child-resistant design, cap with induction seal liner and opening seal ring) and containing a desiccant.

- (Tyvek soft packet, 2 gram silica Gel Desiccant).

- Secondary packaging
- No secondary packaging.

6.2.1.2. *Binimetinib 15 mg film coated tablet*

- **Europe formulation**

- Primary packaging
- 70 film coated tablets will be packaged in a 120 cc bottle (HDPE, without dessicant, white, opaque, square) closed with a cap (38 mm, Polypropylene (PP), white, child-resistant design, cap with induction seal liner).
- Secondary packaging
- The bottle will be packaged in a sealed box.

- **US and Japan formulation**

- Primary packaging
- 70 film coated tablets will be packaged in a 120 cc bottle (HDPE, without desiccant, with induction seal, and child-resistant cap)
- Secondary packaging
- No secondary packaging.

6.2.1.3. *Cetuximab ERBITUX® 5 mg/mL solution for infusion*

- **Europe and Japan formulation: Cetuximab ERBITUX® 5 mg/mL solution for infusion**

- Primary packaging
- 100 mL of solution in a vial (Type I glass) with a stopper (halobutyl rubber) and a seal (aluminium/polypropylene).
- Secondary packaging
- Sealed box of 1 vial: 500 mg.

- **US formulation: Cetuximab ERBITUX® 2 mg/mL solution for infusion**

Erbiximab®(cetuximab) in the US is commercially available. Commercially available vials are packed into cartons.

6.2.2. Labelling

- **Labelling for Europe Supply:**

Investigational Products will be labelled in compliance with local requirements, according to the following rules:

I. Treatment unit box labelling:

The secondary packaging box label (green for binimetinib and white for encorafenib and cetuximab) contains the following information:

- (a) Name and address of Sponsor
- (b) Pharmaceutical dosage form, route of administration, quantity of dosage units, the name/identifier and strength/potency
- (c) Packaging batch number
- (d) Trial reference code allowing identification of the study (protocol number and EudraCT number)
- (e) Treatment number
- (f) Name of the Investigator (will be added when preparing to send)
- (g) Directions for use (reference may be made to the investigator brochure or other explanatory document intended for the trial subject or person administering the product)
- (h) “For clinical trial use only”
- (i) Storage conditions
- (j) Expiry date as month/year (MM/YYYY)
- (k) “Keep out of reach and sight of children” except when the product is for use in trials where the product is not taken home by subjects

The box labelling contains a tear-off flap (also green for binimetinib and white for encorafenib and cetuximab) with the following information:

- Protocol number

- Packaging batch number
- Treatment number
- The name/identifier and strength/potency

Additional mentions will be added according to local authority requirements.

Symbols or pictograms may be included to clarify certain information mentioned above. Additional information, warnings and/or handling instructions may be displayed.

II. Treatment bottle/vial labelling:

The product is supplied in a primary packaging and a secondary packaging which are intended to remain together. The following information is included on the label of the primary package bottle/vial (green for binimetinib and white for encorafenib and cetuximab):

- (a) Name of Sponsor
- (b) Pharmaceutical dosage form, route of administration (may be excluded for oral solid dose forms), quantity of dosage units, the name/identifier and strength/potency
- (c) Packaging batch number
- (d) Trial reference code allowing identification of the study (protocol number)
- (e) Treatment number
- (f) Expiry date as month/year (MM/YYYY)

- **Labelling for US and Japan Supply**

For both encorafenib and binimetinib supplied within the US and Japan, each bottle will be labelled, at a minimum, with a unique identifier (medication number), the lot number, contents (number of tablets), dosage strength, storage conditions and the name and address of the Sponsor designee. Both encorafenib and binimetinib labels will be in the local language and comply with the legal requirements of the US and Japan. Site personnel will add the subject number to the label.

In the US, cetuximab will be supplied either locally or by the Sponsor designee, Array BioPharma.

If the US cetuximab is locally supplied, then the cetuximab does not require specific labelling. Each unit of cetuximab supplied for Japan by the Sponsor designee will be labelled, at a minimum, with a unique identifier (medication number), the lot number, contents (number of tablets), dosage

strength, storage conditions and the name and address of the Sponsor designee. Cetuximab labels will be in local language and comply with the legal requirements of Japan.

6.3. DISTRIBUTION TO CENTERS AND STORAGE

Before the start of the study, the sponsor or designee will supply the Investigational Centre with the necessary treatment units for the study using Interactive Response Technology (IRT).

Additional treatment supplies will be shipped to the Investigational Centre upon request via IRT and according to needs.

Acknowledgement of receipt of all shipments should be managed according to Pharmacy manual process and timelines.

The Clinical Research Associate (CRA) will ensure during the initiation visit that trial medications have been received in good condition and the acknowledgment of receipt has been adequately completed and returned.

In cases of undue delay in study execution, the Pharmacist or Investigator should ensure that the expiry date has not been exceeded. If the date has been exceeded, new treatment units will be supplied to the investigational center.

Labeled, packaged encorafenib, binimetinib and cetuximab will be shipped to each centre by the Sponsor or designee, as described in the Pharmacy Manual.

The Investigator or an approved representative (e.g., registered pharmacist) will ensure that all encorafenib, binimetinib and cetuximab is stored as outlined in the Pharmacy Manual and in accordance with applicable regulatory requirements. The drug storage area at the site must be secure, with access limited to authorized personnel.

Storage conditions will be described on the medication label. Detailed instructions for storage and handling of encorafenib and binimetinib will be provided in the Pharmacy Manual. Cetuximab should be stored according to the locally approved prescribing information.

6.4. ALLOCATION OF TREATMENTS AND DISPENSATION TO SUBJECTS

All subjects who sign an informed consent will be assigned a unique subject number and will be able to start screening. A subject will be assigned for study treatments via the IRT system if he/she meets all eligibility requirements .

According to GCP, all eligibility criteria will be checked during the registration procedure. Assignment of treatment number will be implemented via IRT. All information regarding this process is described in the IRT manual.

Throughout the Treatment Period (Main study and Study extension periods) the Investigator will dispense to the subject the box indicated by IRT (Day 1 of each cycle).

6.5. TREATMENT ADMINISTRATION

6.5.1. Duration of Treatment

During the Main study period, study treatment will be administered until unacceptable toxicity, progression of disease, subject's decision, withdrawal of consent, initiation of subsequent anticancer therapy or death.

During the Study extension period (from 28 Dec 2020), access to study treatment will be provided through a Study extension to all subjects whom the investigator considers are continuing to benefit from study treatment (i.e. do not experience unacceptable toxicities and none of the treatment discontinuation criteria are met) until:

- the last ongoing subject will discontinue study treatments (including 30-day Safety Follow-Up visit) for any reason (unacceptable toxicity, progression of disease, subject's decision, withdrawal of consent, initiation of subsequent anticancer therapy or death),
- or binimetinib/encorafenib are commercially available in the first line setting of *BRAF*^{V600E} mutated mCRC,
- or the binimetinib/encorafenib development program is stopped, whichever comes first.

Dose Schedule

The investigational products in this study are encorafenib and binimetinib in combination with cetuximab. Dose schedule is described in **Table 7**.

Table 7: Dose and Treatment Schedule

Study treatment	Pharmaceutical form and route of administration	Dose	Frequency
Encorafenib	4 × 75 mg oral capsule	300 mg	QD
Binimetinib	3 × 15 mg oral film-coated tablet	45 mg	BID
Cetuximab	IV infusion	400 mg/m ² initial dose (120-minute infusion), then 250 mg/m ² (60-minutes infusion)	QW for the first 28 weeks
		500 mg/m ² (120-minute infusion)	Q2W (from week 29 - C8D1) Since implementation of the Urgent Safety Measure on 26 Mar 2020, in order to ensure the subjects' safety in the clinical trial by decreasing the number of clinic visits in the context of COVID-19 pandemic, Cetuximab infusions can be given every two weeks (i.e. on D1 and D15 of each cycle) regardless of the cycle number, after the investigator has evaluated the benefit/risk ratio for the subject with regards to Covid-19 pandemic.

QD: once daily; BID: twice daily; QW, once weekly; Q2W, every 2 weeks

6.5.2. Route and Conditions of Administration of Encorafenib and Binimetinib

Encorafenib will be administered with a QD schedule and binimetinib will be administered with a BID schedule, both PO as a flat-fixed dose, not by body weight or body surface area (BSA).

Binimetinib and encorafenib can be taken without regard to food. Subjects should be instructed to swallow the capsules /tablets whole and not to chew or crush them. Both oral study drugs are to be taken together in the morning and only the BID administered drug (binimetinib) is to be taken in the evening without regard to food.

- QD dosing: subjects should be instructed to take encorafenib capsules daily with a large glass of water (~250 mL) in the morning (together with the morning intake of binimetinib) at approximately the same time every day. Doses of encorafenib that are omitted for AEs or any other reason can be taken up to 12 hours prior to the next dose; if less than 12 hours to the next dose, the regular dosing schedule must continue and subject should be instructed to check with the study doctor. It is forbidden to double the next dose.
- BID dosing: subjects should be instructed to take binimetinib tablets 12 ± 2 hours apart with a large glass of water (~250 mL) in the morning and in the evening at approximately the same times every day. Doses of binimetinib that are omitted for AEs or any other reason should not be made up later in the day, or at the end of the dosing period and it's forbidden to double the next dose.

On days when a blood collection is scheduled at the investigational site, subjects will take the morning dose of encorafenib and binimetinib at the site under the supervision of the Investigator or designee, after any required blood sample collections. The time of dosing and the time of PK samples should be recorded on these clinic visit dates. On all other days, subjects will take encorafenib and binimetinib at home.

If a subject vomits at any time after dosing, the dose of study drug should not be re-administered. Subjects are prohibited to consume grapefruit, pomegranates, star fruits, Seville oranges or products containing the juice of any of these items throughout the entire study and for 7 days before the first dose of study drugs, due to potential CYP3A4 interaction with the study drugs. Orange juice is allowed.

Encorafenib and binimetinib will be administered at least 30 minutes prior to cetuximab without regard to when cetuximab premedications are administered.

The Investigator or responsible site personnel will ensure that the appropriate dose is dispensed and will provide the subject with at least the appropriate number of encorafenib capsules and binimetinib tablets for the number of doses to be taken prior to the next scheduled visit. The site personnel will train the subject and/or the subject's caregiver on dosing procedures for the study drug.

Subjects will receive a diary to document self-administered dosings of encorafenib and binimetinib for each cycle to include the dose of study drug taken, the date of dosing (and times if applicable), and if any doses were missed and the reason for the missed dose. One diary will be provided per cycle. Subjects will be instructed to return unused encorafenib and binimetinib and the subject diary to the center at the end of each cycle. Drug accountability must be performed on a regular basis.

The Investigator or responsible site personnel should instruct the subject to take encorafenib and binimetinib as per protocol (i.e., promote compliance). The dosage prescribed and dispensed to the subject and all dose changes and all missed doses during the study must be recorded in the e-CRF.

6.5.3. Route and Condition of Administration of Cetuximab

Cetuximab will be administered IV weekly on Days 1, 8, 15 and 22 (± 3 days) of every 28-day cycle at the study center for the first 28 weeks then every two weeks from week 29 (**Table 7**) according to institutional standards.

The initial cetuximab dose on Day 1 of Cycle 1 is 400 mg/m² administered as a 120-minute IV infusion followed thereafter by a 250 mg/m² dose administered as a 60-minute IV infusion at each cycle. Subjects who remain on treatment for 28 weeks will be treated with cetuximab 500 mg/m² administered as a 120-min IV infusion once every 2 weeks from week 29 (Cycle 8 day 1).

Since implementation of the Urgent Safety Measure on 26 Mar 2020, in order to ensure the subjects' safety in the clinical trial by decreasing the number of clinic visits in the context of COVID-19 pandemic, Cetuximab infusions can be given every two weeks at the dose of 500 mg/m² administered as a 120-min IV infusion (i.e. on D1 and D15 of each cycle) regardless of the cycle number, after the investigator has evaluated the benefit/risk ratio for the subject with regards to Covid-19 pandemic.

If there was a dose modification prior to switching to the biweekly schedule, the total dose per cycle should be maintained (i.e. 200mg/m² QW, may be changed to a 400mg/m² Q2W).

The infusion rate should be consistent with local labelling but should not exceed 10 mg/min (the first infusion rate should not exceed 5mg/min). Close monitoring is required during the infusion and for at least 1 hour after the end of the infusion. If an infusion reaction occurs while cetuximab is being administered, the infusion should be stopped immediately, and the subjects should be closely monitored and treated in line with institutional standards. Any re-challenge with cetuximab following an infusion reaction should be first discussed with the Sponsor.

Pre-medication for routine cetuximab infusions may be used in accordance with the label and with the national and/or institutional standards, but should preferably be based on a combination of an H1 antagonist (e.g., diphenhydramine) and dexamethasone (10 mg IV). This combination is mandatory for the first infusion. Pre-medication should be administered no sooner than 1 hour after administration of encorafenib and binimetinib (if applicable) and 30 minutes prior to cetuximab infusion. According to cetuximab labelling instructions, medications such as corticosteroids and antihistamines may be administered at the discretion of the Investigator to treat an existing infusion reaction, or as premedication for a subject who has previously experienced an infusion reaction. Predose PK samples for cetuximab analysis should be collected just prior the beginning of the cetuximab infusion.

Doses of cetuximab that are omitted for AEs or any other reason should not be made up. If cetuximab is discontinued, the frequency of study visits may be decreased after discussion with Sponsor.

6.5.4. Dose Modification

Subjects will be monitored for AEs. The severity of AEs will be evaluated using the NCI-CTCAE v.4.03.

If a subject develops toxicity, the dose should be modified as outlined in **Table 14** and **Table 15**, which include criteria for interruption and reduction of encorafenib, binimetinib and cetuximab. All dose modifications should be based on the worst preceding toxicity. All dosing interruptions and modifications must be recorded in the e-CRF.

If a subject permanently discontinues binimetinib due to an AE or clinically significant laboratory value, they may continue to receive encorafenib in combination with cetuximab.

Due to the lack of efficacy of binimetinib, encorafenib, or cetuximab when used as single agents in subjects with *BRAF*-mutant mCRC, subjects who cannot tolerate these agents in combination with at least one other agent, should discontinue study treatment altogether, complete the end of treatment visit and continue to be followed for survival (and disease progression, if applicable).

Cetuximab may be reduced by 2 dose levels to a minimum of 150 mg/m², due to AEs or laboratory abnormalities (**Table 8**). When a dose reduction is required because of an AE, no subsequent dose re-escalation of cetuximab will be permitted for that subject for the duration of study treatment. If after resolution of an AE, treatment is resumed at the same dose, and the same toxicity reoccurs with the same severity, any re-initiation of treatment must be at the next lower dose level irrespective of duration, with some exceptions for skin toxicity.

In addition, a subject must discontinue study treatment if, after treatment is resumed at a lower dose of cetuximab, the same toxicity reoccurs with the same or worse severity.

If a subject misses > 28 consecutive days of encorafenib or binimetinib, or > 4 consecutive cetuximab doses as the result of an AE or clinically significant laboratory abnormality, then the respective agent(s) should be discontinued.

Subjects who discontinue study treatment for a study-related AE or an abnormal laboratory value must complete the end of treatment visit and continue to be followed for survival (and disease progression).

Table 8: Dose Levels for Dose Modification

	Encorafenib (mg QD)	Binimetinib (mg BID)	Cetuximab WEEKLY (mg/m²)	Cetuximab BI-WEEKLY (mg/m²) Starting from C8D1 week 29 Or at any cycle since implementation of the Urgent Safety Measure on 26 Mar 2020
Starting Dose	300	45	400 mg/m² cycle 1 day 1 then 250 mg/m² thereafter	500
Dose level -1	225	30	200	400
Dose level -2	150	15	150	300

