6.5.4.2. Dose Modifications for Cetuximab

Recommended dose modifications for cetuximab based on the occurrence of cetuximab treatment-related AEs are summarized in **Table 15**. **Section 17.1** contains recommended guidelines for prophylactic and symptomatic treatment of cetuximab-induced rash.

Table 15: Recommended dose modifications for Cetuximab during a cycle of therapy

Worst toxicity CTCAE, v.4.03 Grade	Dose Modification for Cetuximab During a Cycle of Therapy
Infusion Reaction	If an infusion reaction occurs while cetuximab is being infused, the infusion should be stopped immediately and the subject should be evaluated.
Grade 1 or 2	Restart and complete the disrupted infusion at the discretion of the Investigator. The infusion must be restarted at a reduced rate. Additional pre-medications such as antihistamines or low-dose systemic corticosteroids may be administered when the infusion is restarted per institutional standards. All subsequent infusions must also be administered at the reduced rate.
Grade 3 or 4	Permanently discontinue cetuximab
Rash: see encorafenib and/or binimetinib dose modifications (Table 14)	
Grade 1 or 2	Maintain dose level; consider initiating appropriate therapy (such as antihistamines, topical corticosteroids, and low-dose systemic corticosteroids)
Grade 3, despite therapy	Omit dose until resolved to \leq Grade 2, then: 
 • If resolved in \leq 7 days (or \leq 14 days for acneiform rash), then maintain dose level • If not resolved in \leq 7 days despite appropriate skin toxicity therapy (or \leq 14 days for acneiform rash), then permanently discontinue cetuximab
Grade 3 recurrent	Omit dose until resolved to \leq Grade 2, then: 
 • If resolved in \leq 7 days (or \leq 14 days for acneiform rash), then decrease 1 dose level • If not resolved in \leq 7 days despite appropriate skin toxicity therapy (or \leq 14 days for acneiform rash), then permanently discontinue cetuximab • Permanently discontinue cetuximab after 3rd recurrence (i.e., upon 4th occurrence)
Grade 4, despite skin toxicity therapy	Permanently discontinue cetuximab
Interstitial lung disease - Section 17.7 : in case of ILD, for all grades, cetuximab must be discontinued	

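### At a third Grade 3 rash, on an already reduced cetuximab dose, Protocol Section 6.5.4 orders a stop while Table 15 orders a further reduction

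*Protocol*

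**What the plan says.** Section 6.5.4 of the protocol opens by sending the reader to the tables: "If a subject develops toxicity, the dose should be modified as outlined in" Tables 14 and 15. It then gives general rules for cetuximab in running text.

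- On the number of reductions: "Cetuximab may be reduced by 2 dose levels to a minimum of 150 mg/m², due to AEs or laboratory abnormalities".
- On a toxicity that returns at the same severity after treatment was resumed at an unchanged dose: "any re-initiation of treatment must be at the next lower dose level irrespective of duration, with some exceptions for skin toxicity".
- In a new paragraph, on a toxicity that returns after the dose was lowered: "must discontinue study treatment if, after treatment is resumed at a lower dose of cetuximab, the same toxicity reoccurs". The rule applies when the recurrence is at least as severe as before.

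Table 15, in Section 6.5.4.2, has its own rows for rash. A Grade 3 rash despite therapy means that cetuximab is withheld until Grade 2 or lower. If that happens within 7 days (14 for acneiform rash), the dose is kept; if not, cetuximab is permanently stopped. Recurrent Grade 3 rash is handled with the same time limits, except that timely resolution leads to a decrease of one dose level. The row ends with: "Permanently discontinue cetuximab after 3rd recurrence (i.e., upon 4th occurrence").

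**The concern.** The same patient can fall under both rules, and both are current text. A patient whose cetuximab was lowered after a second Grade 3 rash, and who then has a third, meets the condition of the mandatory stop in Section 6.5.4: same toxicity, same severity, reduced dose. Table 15 treats that third episode as one more recurrence to be answered with a further reduction.

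The texts also name different things to stop. Section 6.5.4 speaks of study treatment; Table 15 speaks of cetuximab. If sites follow different passages, stopping decisions for the same event will differ between sites, and so will exposure and the tables of adverse events leading to discontinuation.

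**Working it through.** No formula applies. The check is to step each rule through successive Grade 3 rash episodes.

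**Inputs**
- Cetuximab dose levels from Table 8: weekly 250, 200, 150 mg/m²; every two weeks 500, 400, 300 mg/m².
- Two reductions allowed (Section 6.5.4).
- Table 15 rows for Grade 3 and recurrent Grade 3 rash.
- Assumption: every episode resolves to Grade 2 or lower within Table 15's limit of 7 days, or 14 for acneiform rash.

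**Result** (weekly dose, with the two-weekly dose in brackets)

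| Grade 3 rash | Dose at onset, mg/m² | Table 15 | Section 6.5.4 text |
|---|---|---|---|
| 1st | 250 (500) | keep dose | same dose possible |
| 2nd | 250 (500) | resume at 200 (400) | resume at 200 (400) |
| 3rd | 200 (400) | resume at 150 (300) | discontinue study treatment |
| 4th | 150 (300) | stop cetuximab | not reached |

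The Table 15 column reproduces the table's own stopping point, the fourth occurrence, and uses exactly the two reductions allowed: 250 to 200, then 200 to 150. The columns agree for the first two episodes and part at the third. Under the Section 6.5.4 text, the second reduction for rash and the fourth occurrence cannot be reached.

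**Does the skin-toxicity exception cover the gap?** It is attached to the rule for recurrence at an unchanged dose, where re-starting "must be at the next lower dose level irrespective of duration, with some exceptions for skin toxicity". The stop rule is a separate paragraph, added to that one, and carries no exception. Section 6.5.4 does not say what the exceptions are.

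**Does either text take precedence?** Section 6.5.4 uses mandatory wording, and Table 15 is titled as recommendations. Against that, Section 6.5.4 itself directs that doses be modified according to Table 15. Neither place says which governs if they differ.

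**What stops?** SAP Section 9.1.1 defines study treatment as the combination of encorafenib, binimetinib and cetuximab. The protocol is less uniform. Section 6.5.4 adds the word *altogether* where it plainly means the whole regimen, and in the paragraph after the stop rule it refers to the *respective* agents. Table 7 has a column headed study treatment that lists the three drugs one by one. Table 14 lets encorafenib and binimetinib resume after a second Grade 3 rash and calls for permanent discontinuation only at Grade 4.

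**How many patients?** Section 1.2.3 reports, for the same triplet in the BEACON CRC safety lead-in, one Grade 3/4 skin event, a Grade 3 rash, in 30 patients (1/30 = 3.3%). Table 3 shows no Grade 3/4 rash among 50 patients on encorafenib plus cetuximab. Patients with three qualifying episodes can only be a subset of those with any Grade 3 rash.

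**The case against.** The best reply is that the documents point to the rash-specific rule. Section 6.5.4 begins by deferring to the tables, Table 15 is the only place that deals with recurrent Grade 3 rash, and the sentence just before the stop rule signals exceptions for skin toxicity. On this view the exception does little where it stands, because Table 15 also lowers the dose by one level at the second episode. It must therefore have been meant for the stop rule, and the problem is misplaced wording.

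That may be what was intended, but it is inference. The exception also has some work to do where it stands: the sentence disregards duration, while Table 15 makes continuation depend on resolution within 7 or 14 days. As written, the stop rule has no exception, so the conflict at the third episode remains.

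Three parts of the reply do stand.
- The conflict is conditional. A Grade 3 rash that misses the time limit stops cetuximab under Table 15 at any episode, including the first. The rules part only for a patient with three Grade 3 episodes that each settle in time.
- A reader might infer that Section 6.5.4 certainly ends all three drugs. The SAP definition supports that reading, but the protocol's own usage also allows a cetuximab-only reading. The scope is unclear, not settled.
- A reader might infer that the choice of rule changes the confirmed response rate, because SAP Section 14.1 counts only assessments up to 30 days after last study treatment. That route needs the three-drug reading, since last administration means the last dose of any study drug (SAP Section 9.1.2). It also needs a patient with an unconfirmed response at a third qualifying episode. The documents give no figure for this, so no effect on the primary endpoint is claimed.

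**Conclusion.** The inconsistency is real and narrow. Under the stated assumption that each episode resolves within Table 15's limit, Section 6.5.4 and Table 15 agree for the first two Grade 3 rash episodes and give incompatible instructions at the third. The difference is one occurrence and one dose level. Which drug or drugs stop is a second, separate ambiguity.

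Few patients are likely to be affected. The protocol's description of skin reactions as a main side effect of cetuximab covers all grades and should not be read as a rate of recurrent Grade 3 rash. The point still merits correction because it concerns a mandatory stopping rule on which sites could act differently.

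**What to change.** Reconcile Section 6.5.4 and Table 15 so that both state the same three things: whether the recurrence stop rule applies to rash, at which occurrence treatment stops, and whether the stop covers cetuximab alone or all study drugs. If skin toxicity is to be excepted anywhere, say from which rule, and point to the row that replaces it. No view is taken on which rule is right.

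The change is to wording, with no effect on sample size or analysis methods. It does need a protocol amendment, and Section 15.1 requires submission to ethics committees and authorities if the amendment is substantial. The benefit is limited to subjects still on treatment: the last enrolled subject started on 27 December 2019 and this protocol version is dated 17 July 2020. The text remains in force for them, because Section 4.1 carries the dose modification recommendations into the Study extension period.
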